The Injunctive Norms Questionnaire (Baer, 1994) assessed participants' personal approval and perceptions of the approval of a typical same-sex first-year student at their specific university for five risky drinking behaviors including "playing drinking games," "drinking shots," "drinking to get drunk," "drinking alcohol every weekend," and "drinking under age 21." Response options ranged from 1 (*strongly disapprove*) to 7 (*strongly approve*). Internal consistency was high in $\alpha = .89$ for and responses were averaged to create a composite score.

Heaviest Drinking Occasion (Peak Drinks)

Participants were instructed to think about their drinking in the past 30 days and respond to the question, "What is the maximum number of drinks you drank during any one drinking occasion?" Values were truncated at 30.

Typical Weekly Drinking

Typical drinking was measured using the Daily Drinking Questionnaire (Collins et al., 1985). Participants were asked to report the number of standard drinks they consumed on each day (e.g., a typical Monday, Tuesday) of the week during the past 30 days. Responses were summed across the 7 days, and the sums were truncated at 80.

Alcohol-Related Problems

Problems arising from alcohol use were measured using the Brief Young Adult Alcohol Consequences Questionnaire (Kahler et al., 2005). Participants indicated (no=0, yes=1). if they

had experienced 24 negative experiences after drinking alcohol (e.g., “I have felt very sick to my stomach or thrown up after drinking”). Responses were summed, with total scores ranging from 0 to 24. Cronbach’s alphas were acceptable across the four timepoints ($\alpha=0.89-0.92$).

App Measures

Number of Game Feedbacks Viewed

Whether or not participants viewed each round of game feedback was recorded in the app’s backend. This allowed us to create variables indicative of (1) the total number of feedback viewed; and (2) the number of alcohol-specific feedback viewed.

Statistical Analysis Plan

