A preliminary examination of the outcome distributions revealed that a large proportion of the sample did not drink, and the distributions of outcomes were all positively skewed. A generalized linear mixed modeling approach was used for all analyses. Given the large proportion of non-drinkers, we conducted hurdle-negative binomial mixed models to evaluate peak drinks and alcohol-related problems. Hurdle models are two-part models that independently predict zero versus non-zero counts in one part and values of non-zero counts in the other (Cameron & Trivedi, 2013; Hilbe, 2011). For peak drinks, the zero versus non-zero part of the model predicts whether individuals drank any alcohol using a logistic mixed model. The non-zero counts part of the model uses a truncated (i.e., zeros are removed, and values are subtracted by one) negative binomial mixed model to predict the number of alcoholic beverages consumed during drinkers’ heaviest occasion. Similarly, for alcohol-related problems, whether individuals experienced any alcohol-related problems or not was evaluated with a logistic mixed model, and the number of problems among those who experienced any was examined with a truncated negative binomial mixed model. Analyses examining the typical number of drinks consumed per week focused exclusively on counts, using a truncated negative binomial model; this approach avoided duplicating the logistic part of the peak drinks analysis, which would have occurred if zero versus non-zero values were compared, as this would have resulted in less precision.

Modeling Treatment. The intervention was evaluated using two strategies. The first evaluated conditions using an intent-to-treat (ITT) approach, in which outcomes were analyzed based on condition assignment, regardless of treatment participation and adherence (McCoy, 2017). Extending the short-term analyses presented in LaBrie et al. (2025), the second strategy evaluated outcomes at follow-up as a function of the number of alcohol feedbacks viewed (i.e., 0-6), which helped to eliminate the noise associated with variability in number of alcohol feedbacks viewed within LAF and MAF conditions.

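### Typical weekly drinks is compared between arms only among students who report drinking after randomization, and no analysis of this outcome covers everyone randomized

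*Combined protocol and SAP*

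**What the plan says.** The Design section lists drinks in a typical week among the consumption outcomes, measured at 4, 9 and 12 months. For peak drinks and alcohol-related problems the Statistical Analysis Plan specifies two-part hurdle models. For peak drinks, "the zero versus non-zero part of the model predicts whether individuals drank any alcohol using a logistic mixed model", and the count part "uses a truncated (i.e., zeros are removed, and values are subtracted by one) negative binomial mixed model". For problems there is a logistic part for any problem, and "the number of problems among those who experienced any was examined with a truncated negative binomial mixed model".

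Weekly drinks gets the second part only: "Analyses examining the typical number of drinks consumed per week focused exclusively on counts, using a truncated negative binomial model". The reason given is that "this approach avoided duplicating the logistic part of the peak drinks analysis". Of that duplication the plan then says: "which would have occurred if zero versus non-zero values were compared, as this would have resulted in less precision".

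Under Modeling Treatment the primary strategy is called intent-to-treat, meaning that "outcomes were analyzed based on condition assignment, regardless of treatment participation and adherence". Modeling Time adds that every enrolled participant's data entered the analyses, with adjustment for baseline value, sex, site and time point. Neither paragraph describes an overall mean that combines the two hurdle parts, or any caveat on the count comparisons.

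**The concern.** Whether a student drinks at follow-up is itself an outcome. The Goals section expects less frequent feedback to do better at preventing initiation, and the Power paragraph sizes the trial partly on abstinence. The students left after zeros are dropped may therefore be differently selected groups in the three arms. Urn balancing on baseline drinking protects the arms as randomized; it does not protect the subset drinking months later.

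At stake is the interpretation of a named outcome. If feedback keeps would-be light drinkers abstinent, the remaining drinkers in that arm look heavier and the count ratio shifts against feedback. If feedback adds light drinkers, the ratio shifts in its favor. Peak drinks and problems at least have logistic parts that retain the zeros. Weekly drinks has nothing of that kind.

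**Working it through.** The plan gives no figure for this effect, so there is none to reproduce. The power figures of .89 and .87 play no part in the argument.

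**Inputs**
- Control abstinence of 30%: Power paragraph.
- A shift of 5 points: size taken from the Power paragraph, which words it as abstinence lower than control. Steps 1 and 2 use the protective direction hypothesized in the Goals section; step 3 uses the other.
- Mean of 6 drinks a week among control drinkers, and 2 among those whom feedback keeps abstinent: assumptions. The documents give no means.
- r, the ratio of amounts in continuing drinkers, feedback to control: varied.

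**Step 1. No effect on amount (r = 1), per 100 students.** Control has 70 drinkers and 70 × 6 = 420 drinks, an overall mean of 4.20. Under feedback 65 drinkers remain, with 420 − 5 × 2 = 410 drinks.
- Drinkers' mean: 410/65 = 6.308, so the drinkers-only ratio is 6.308/6 = 1.05.
- Overall mean: 410/100 = 4.10, so the overall ratio is 4.10/4.20 = 0.976.

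**Step 2. With an effect on continuing drinkers.** Both ratios are multiplied by r.

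| r | Drinkers-only ratio | Overall ratio |
|---|---|---|
| 1 | 1.05 | 0.976 |
| 0.95 | 6.308 × 0.95 / 6 = 5.99/6, about 1.00 | 0.976 × 0.95 = 0.927 |
| 1/1.2 (the plan's target ratio) | 6.308 / 1.2 / 6 = 0.88 | 0.976 / 1.2 = 0.81 |

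The drinkers-only ratio exceeds 1 only if r is above 6/6.308 = 0.951. Below that the direction is right, but the effect looks smaller than the overall one.

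**Step 3. Opposite direction.** Feedback adds 5 points of drinkers who average 2. The drinkers' mean is (420 + 10)/75 = 5.73, a ratio of 0.956 (apparent benefit), while the overall mean rises to 4.30, a ratio of 4.30/4.20 = 1.024.

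**Step 4. Sensitivity to the assumed means.** Let continuing drinkers average 8 in both arms. With 2 to 10 points more abstinence, and those kept abstinent otherwise at 1 to 4 drinks, the drinkers-only ratio runs from 1.014 to 1.143 and the overall ratio from 0.923 to 0.996. If those kept abstinent would also have averaged 8, the drinkers-only ratio is 1.00 and there is no distortion of the conditional mean.

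**Step 5. Baseline adjustment.** A simulation of the truncated count model (400 per arm, 300 runs, no effect on amount, assumed data) gave these ratios:

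| Extra abstinence | Drinkers-only, unadjusted | Drinkers-only, adjusted | Overall |
|---|---|---|---|
| 0 points | 1.005 | 1.001 | about 1.01 |
| 5 points | 1.036 | 1.025 | 0.96 |
| 10 points | 1.077 | 1.051 | 0.91 to 0.92 |

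Adjustment shrinks the bias without removing it. The plan itself assumes that baseline explains only 25% of the variance in any drinking at follow-up.

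**Step 6. The stated reason.** The plan describes the two hurdle parts as predicting independently of each other. Leaving out the zero part then adds no precision to the count part. Nor would the zero part exactly repeat the one for peak drinks. Peak is the most drunk on any single occasion in the past 30 days, whereas for the weekly measure students "report the number of standard drinks they consumed on each day" of a typical week. A student who drank once in the month can have a peak above zero and a typical week of zero. That student counts as a drinker in the peak analysis and drops out of the weekly one.

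**The case against.** Hurdle models are standard for such data, and an effect on amount given drinking is a legitimate quantity. The peak-drinks logistic part tests any drinking by randomized arm, so a reader would see an abstinence effect beside the weekly ratio. The analysis also meets the plan's own definition of intent-to-treat, which concerns assignment and adherence. All of this stands. It does not supply a comparison of weekly drinks in everyone randomized, and the peak proxy is inexact to a degree that the documents do not let us measure.

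Four stronger readings are tempting and are not supported:
- **That all three outcomes lack a randomized comparison.** For peak drinks and problems the logistic parts keep the zeros and compare the arms as randomized. Only their count parts are conditional, and the one for problems is conditional on any problem, not on drinking.
- **That the sign reverses whenever those kept abstinent would have been lighter drinkers.** Step 2 shows that the effect on continuing drinkers must also be small.
- **That 30% of each arm is excluded.** The 30% is a planning assumption. Exclusion is by observation, so a student with zero at one wave can contribute at another. Equal arms cannot be assumed for a head count either: the Procedure section's figures imply about 130/0.31 = 419 and 137/0.37 = 370 in the two feedback arms, leaving about 354 of 1,143.
- **That the 5-point rise in abstinence is the plan's own effect.** The plan words its 5% as a reduction; only the size is borrowed here.

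**Conclusion.** The concern holds for weekly drinks. Its only between-arm comparison is conditioned on a post-randomization outcome that the intervention is expected to change, and this conflicts with the Modeling Time statement about all enrolled participants. For peak drinks and problems the issue is one of labelling and of a missing overall contrast.

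The likely distortion is modest. The ratio is 1.05 under the stated assumptions, against the 1.2 that the trial was powered to detect, and adjustment reduces the bias. A misleading sign is possible, not certain. It needs an effect on who drinks, marginal drinkers who are lighter than the rest, and little effect on the others. The means of 6, 2 and 8 are assumptions. The structural finding does not depend on them.

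**What to change.** - **Weekly drinks:** add the zero part. Report an all-randomized contrast (ratio and difference) of overall mean weekly drinks, computed as P(non-zero) × mean given non-zero. Integrate over the random effects and give bootstrap or delta-method intervals. If counts are modeled after subtracting one, restore it before forming the mean. State that this analysis was added after the outcome distributions had been examined.
- **Peak drinks and problems:** keep the hurdle models and add the same overall-mean contrast as a supplement. Label the count-part ratios as conditional on a non-zero outcome (any drinking or any problem, respectively) and not as randomized contrasts.
- **Text:** delete the precision rationale, and reconcile the removal of zeros with the statement that all enrolled participants were analyzed.

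The cost is one additional logistic model, moderate computation (integrating over random effects and carrying uncertainty across two parts is more than routine post-estimation) and some rewording. No new data are needed. The drawback is that the added contrast is post hoc and must be reported as such.

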Building on this work and in response to calls in the literature to explicitly examine changes in perceived drinking norms and alcohol outcomes in PNF intervention studies (e.g., Dempsey et al., 2018), this study employed a large and diverse sample of incoming college students attending universities in Texas and California to (1) examine the effectiveness of a fully featured CampusGandr smartphone app as an alcohol intervention strategy when advertised to students as a social game about college life free to play over their fall semester; and, (2) elucidate the optimal dosage of alcohol feedback to be delivered in the app to best reduce perceptions of drinking norms and alcohol consumption. First, using an intent-to-treat approach, we examine short and longer-term effects on alcohol use and perceptions of drinking norms associated with a CampusGandr intervention period in which student users were randomized to receive alcohol feedback in 0, 3, or 6 weeks of the game. Second, we take a closer look at the question of dosage by examining end-of-semester drinking and perceptions of norms as a function of the number of alcohol feedback results verifiably viewed by participants. Whereas a traditional alcohol intervention approach might assume that delivering alcohol feedback every week would be most protective, our pilot work (Boyle et al., 2018) and a large psychological reactance literature (e.g., Dillard et al., 2023; Jung et al., 2010; Reynolds-Tylus et al., 2022, 2024) suggest that too much feedback on alcohol relative to other topics in the game may reveal the drinking-reduction intention of the activity, eliciting reactance, and thereby undermining efficacy. As such, less frequent alcohol feedback balanced with feedback on other topics of interest to students was expected to be more efficacious in reducing perceived drinking norms, preventing alcohol

initiation, and reducing consumption than both no alcohol feedback and more frequent alcohol feedback.

Design

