In total 2,898 students consented and then took the baseline survey and/or played CampusGandr. Of those, 1,143 students were considered fully enrolled in the study, as they provided consent, completed the baseline survey, and played at least one round of CampusGandr. Participants were randomized using an automated urn strategy so that each of the three conditions were filled evenly by a gender and baseline drinking status (any, none). All PNFs were delivered remotely and automatically; therefore, participants, but not researchers, were blind to allocation. Based on condition assignment, participants could see up to 6 alcohol feedbacks (More Alcohol Feedback; MAF), up to 3 alcohol feedbacks (Less Alcohol Feedbacks; LAF) or 0 alcohol feedbacks (No Alcohol Feedback; NAF) during the weekly game. Participants were unaware of study condition, and randomization was not based on any variables. Condition assignment to the LAF and MAF conditions did not guarantee that the participants played the round (i.e., estimating their peers' answer and providing their own answer) and viewed the results (i.e., PNF). Approximately 31% ($n=130$) of participants in the MAF condition saw all 6 alcohol feedbacks and 37% ($n=137$) of participants in the LAF condition saw all 3 alcohol feedbacks. On average, participants in the MAF condition saw 3.0 alcohol feedbacks ($SD=2.6$), and participants in the LAF condition saw 1.5 alcohol feedbacks ($SD=1.3$).

Survey Measures

Descriptive Drinking Norms

Estimates of peers' drinking quantity was measured using the Drinking Norms Rating Form (Baer, 1994). Participants reported the number of standard drinks they believed that a same-gender peer consumed on each day of the week (e.g., a typical Friday, a typical Saturday) in the past 30 days. Participants were asked to think about, "a typical [*male/female/student*] at [*specific college name*]" when answering. Responses were summed across the 7 days, and the sums were truncated at 80.

Injunctive Drinking Norms

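### The feedbacks-viewed analysis takes about two thirds of its dose variation from post-randomisation viewing and names no covariate for engagement, so it is observational and should be labelled and adjusted as such

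*Combined protocol and SAP*

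**What the plan says.** Under Goals of This Clinical Trial, "student users were randomized to receive alcohol feedback in 0, 3, or 6 weeks of the game". The same section announces a second look at dosage, "examining end-of-semester drinking and perceptions of norms as a function of the number of alcohol feedback results verifiably viewed by participants".

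The SAP (Modeling Treatment) sets out two strategies. "The first evaluated conditions using an intent-to-treat (ITT) approach". Then "the second strategy evaluated outcomes at follow-up as a function of the number of alcohol feedbacks viewed (i.e., 0-6"), with the reason "which helped to eliminate the noise associated with variability in number of alcohol feedbacks viewed within LAF and MAF conditions".

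The Procedure section makes clear that the schedule assigned is not the number viewed: "Condition assignment to the LAF and MAF conditions did not guarantee that the participants played the round" or looked at the results. On average "participants in the MAF condition saw 3.0 alcohol feedbacks" out of a possible six.

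Modeling Time lists the covariates as baseline values, sex, site and follow-up time point. App Measures says the app also recorded "the total number of feedback viewed", but no described model includes it. For the second strategy the SAP names no assigned-arm term, no instrument and no other method for non-randomised exposure. It gives no caveat that the comparison is not randomised.

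**The concern.** Only the schedule of 0, 3 or 6 alcohol weeks was randomised. How many results a student opened is behaviour after assignment. Within the less-feedback (LAF) and more-feedback (MAF) arms, the count mainly separates students who stayed in the game from those who drifted away.

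The scale also mixes unlike groups. Zero pools every no-feedback (NAF) control, however engaged, with LAF and MAF students who opened nothing. Counts of four to six can occur only in MAF students who viewed most of their results.

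If students who stay engaged drink less, or more, for reasons beyond baseline drinking, sex and site, the association with number viewed can show a dose effect that does not exist or hide one that does. The plan looks to this analysis for a closer answer on dosage, so an unlabelled association could be read as evidence on how much alcohol feedback to deliver.

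**Working it through.** **Inputs (Procedure).** 1,143 enrolled. MAF: mean 3.0, SD 2.6, 130 (about 31%) saw all six. LAF: mean 1.5, SD 1.3, 137 (37%) saw all three. NAF: 0 by design. The Power paragraph concerns abstinence rates and rate ratios between conditions and gives nothing for the viewed-count analysis, so there is no plan figure to reproduce.

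**Step 1: implied arm sizes.** MAF 130/0.31 ≈ 419; LAF 137/0.37 ≈ 370; NAF 1,143 − 419 − 370 = 354.

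**Step 2: variance of number viewed.**
- Overall mean = (419×3.0 + 370×1.5)/1,143 = 1.585.
- Within arms = (419×2.6² + 370×1.3²)/1,143 = 3.025.
- Between arms = [419×(3.0−1.585)² + 370×(1.5−1.585)² + 354×(0−1.585)²]/1,143 = 1.514.
- Within-arm share = 3.025/(3.025 + 1.514) = 66.6%.
- With equal arms: within (0 + 1.69 + 6.76)/3 = 2.817, between (2.25 + 0 + 2.25)/3 = 1.50, share 65.3%.
- Rounding in the inputs gives 63-69%. Among LAF and MAF alone the share is 89%.

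**Step 3: could the in-game spinner explain it?** The spinner picks two of three questions. Independent 2/3 draws would give (2/3)⁶ = 9% of MAF seeing all six, against 31% stated. Binomial variance at the observed means is 6×0.25 = 1.5 (MAF) and 3×0.25 = 0.75 (LAF), against 6.76 and 1.69. Subtracting that much chance variance, (419×1.5 + 370×0.75)/1,143 = 0.793, leaves (3.025 − 0.793)/4.539 = 49% of the total, against 33% randomised. An SD of 2.6 on a 0-6 range with mean 3.0 (maximum possible 3.0) is close to all-or-none viewing.

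**Step 4: consequence when there is no true effect.** Simulated trials of 1,143 students used a linear outcome. A viewing probability of Beta(.22, .22) gave MAF mean 3.0, SD 2.59, 33% seeing all six, and LAF mean 1.5, SD 1.34, 39% seeing all three. The correlation is between engagement and outcome after baseline adjustment, and it is an assumption. A variant included a baseline covariate explaining 25% of outcome variance, the SAP's own power assumption for any drinking. The table shows rejection at nominal 5%; ranges cover repeated runs and set-ups.

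| Assumed correlation | Number viewed alone | Plus noisy engagement proxy (error SD 2.5 views, assumed) |
|---|---|---|
| .05 | 18-19% | 9-10% |
| .10 | 51-55% | 19-21% |
| .15 | 87-88% | 39-40% |

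- With zero correlation, number viewed alone rejects at 4-5%.
- Using assigned condition as instrument gives about 4-7%.
- Adjusting for a near-perfect engagement proxy gives 3-6%, which is a best case.
- A separate set-up with correlations of −.1, −.2 and −.3 gave 47%, 98% and 100% for number viewed alone, with the intent-to-treat arm trend at about 4-5%. At −.1 the mean spurious slope was −0.026 SD per feedback, or 6×0.026 = 0.16 SD between zero and six views.

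**Step 5: price of using only randomised variation.** The ratio of standard errors is about √(total/between) = √(4.539/1.514) = 1.73, or √(4.317/1.50) = 1.70 with equal arms.

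**The case against.** The strongest reply is that the randomised analysis comes first and is sound. The hypothesis that less feedback beats both none and more is exactly LAF against NAF and LAF against MAF, and both contrasts are in the intent-to-treat strategy. This stands. A reader might infer that the dosage goal rests only on the viewed count; the Goals section does not support that.

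Other strong readings also fail:

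- **That the dose conclusion is confounded.** The documents report no dose result, so the size and direction of any bias are unknown.
- **That the plan fits one straight line over 0-6 and so cannot test its hypothesis.** The functional form is not stated; linear, quadratic and categorical forms all fit the wording.
- **That the unadjusted intervals are too narrow.** In simulation the model standard error was accurate (mean 0.0142, empirical SD 0.0137-0.0145). The fault is bias.
- **That a quadratic instrumental-variable model would settle whether less beats more.** Three arms give two instruments for two terms, so the model only rescales the intent-to-treat contrasts. Mean squared counts are 1.3² + 1.5² = 3.94 and 2.6² + 3.0² = 15.76. The quadratic coefficient is therefore (MAF effect − 2×LAF effect)/(15.76 − 2×3.94), or 0.127 times that contrast. With equal arms, its standard error for six against three views is 0.193 SD, against 0.072 SD for MAF against LAF.

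It is also fair to say that baseline adjustment removes some confounding, that only the first step of the models is described, that the correlations are assumed, and that a linear outcome stands in for the hurdle models. None of this rescues the noise rationale or supplies the missing engagement covariate and caveat.

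**Conclusion.** The concern holds for the second strategy only. Number viewed is a post-randomisation behaviour, about 65-67% of its variance is not randomised, and no stated covariate measures engagement. The analysis is therefore open to confounding that the plan does not address. The stated rationale is wrong because the model uses within-arm viewing as exposure.

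The variance share rests on the document's own figures. The false-positive rates rest on assumed residual correlations of .05 to .15 and a linear outcome; they show that a small correlation is enough, not that one exists. The intent-to-treat analysis remains the randomised evidence on 0, 3 and 6 weeks. If a later modelling step already adjusts for engagement, the SAP should say so.

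**What to change.** 1. Delete the statement that the viewed-count analysis helps to remove noise.
2. Label that analysis observational and secondary to intent-to-treat for the dosage conclusion, and state its functional form.
3. Adjust it for rounds played before week 9, which precede any alcohol feedback.
4. As a sensitivity analysis, adjust also for total feedback viewed in the alcohol-feedback weeks. State that this measure is itself post-randomisation and an imperfect proxy, so it reduces bias without necessarily removing it.
5. Add a supportive instrumental-variable analysis with assigned condition as instrument for number viewed. State that it assumes assignment acts only through number viewed, which the plan's reactance argument about the balance of topics strains. State also that in the truncated count parts it conditions on a non-zero outcome that arises after randomisation.

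The cost is SAP wording and a modest re-run, provided the app's round-level records are held as App Measures indicates. Instrumental-variable intervals will be about 1.7 times as wide as the unadjusted ones, because only the randomised part of the dose variation is used.
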